4.5.6. Summary of Continuous Glucose Monitoring Wear Time

Summary of CGM wear time will be presented in a table by study period and correlated with MBD data.

4.5.7. Hypoglycaemia Fear Survey – Short Form Questionnaire Score

Hypoglycaemia Fear Survey – Short Form (HFS-SF) Questionnaire score will be summarized at Visit 1 and Visit 7 and change will be calculated. Scores will be analyzed with MBD data using Spearman correlation.

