#### **Exploratory:**

- 1) Summary statistics of actual and change in HbA1c between baseline and Visit 7
- 2) Outcome of IORW HCP questionnaires
- 3) Outcome of IORW participant questionnaires
- 4) CGM curves integrated with data received from the Tempo Pen/Smart Button
- 5) Glooko Mobile App data (e.g., number of connections to the app, number of uploads from CGM, number of CCL data uploads, % of CGM data available, number of insulin data available) and comparison of Study Period 1 and Study Period 2 app use
- 6) Summary of CGM wear time data and correlation with MBD data and differences between Study Period 1 versus Study Period 2
- 7) HFS-SF questionnaire score between Visit 1 and Visit 7 and MBD data.
- 8) Summarize nighttime (00:00 AM to 06:00 AM) and daytime CGM profiles during the masked/ unmasked periods.

Abbreviations: B = breakfast; CGM = continuous glucose monitoring; D = dinner; HbA1c = glycated haemoglobin; HCP = healthcare professional; IORW = Study F3Z-MC-IORW; L = lunch; MBD = missed bolus dose; MDSW = medical device software; TAR = time above range; TBR = time below range; TIR = time-in-range.

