Site personnel will review hypoglycaemia management and provide appropriate training to participants (see Section 2.4.3.1).

For a complete list of all required activities, please refer to the SoA (Table 1.1).

#### 4.2.3. Visit 2 - Remote Check-in 1

Visit 2 will be conducted approximately 1 week after Visit 1. Site will perform a remote check-in in which they will review the understanding and use of the study components with participants.

During the visit, the site staff will:

- collect DDs
- collect AEs
- review concomitant medications/changes in medications
- review the functioning, understanding, and use of the study platform components, and
- confirm up-to-date participant CGM and Tempo Pen/Smart Button data was uploaded to the RMA

For a complete list of all required activities, please refer to the SoA (Table 1.1).

## 4.2.4. Visit 3 - In-Person Check-in 1

Visit 3 will be conducted approximately 5 weeks after Visit 2.

At Visit 3, the participant will be required to visit the study site with his/her:

- mobile device with RMA
- CGM
- Dexcom receiver
- Tempo Pen(s) currently in use, and
- Tempo Smart Button.

Unused Tempo Pen(s) may remain at the participant's residence so long as he/she checks how much is remaining to aid in resupply calculations.

During the visit, the site staff will:

- collect DDs
- collect AEs
- review concomitant medications/changes in medications
- review study supplies and dispense, as needed
- review the functioning, understanding, and use of the study platform components
- confirm up-to-date participant CGM data was uploaded to the RMA
- administer IORW Participant V3 Questionnaire
- administer HFS-SF Questionnaire, and
- weigh the participant.

For a complete list of all required activities, please refer to the SoA (Table 1.1).

In addition, following completion of the IORW Participant Visit 3 Questionnaire and HFS-SF Questionnaire, the site staff will unmask the CC data, review the participants' dosing patterns, and discuss information from the HCP Portal with the participant about his/her dosing habits and glucose control collected during Study Period 1.

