#### 6.3. Measures to Minimise Bias

This is an open-label, single-arm, pragmatic study in which all study participants will be receiving insulin lispro 100 units/mL (Humalog) via Tempo Pen. Study participants and study personnel will not be blinded to insulin treatment or study devices. Study participants who meet all inclusion/ exclusion criteria (Sections 5.1 and 5.2) will be enrolled into the study at Visit 1 (Week 0).

To minimise the bias, study participants will be used as their own control by designing the study to include two study periods: Study Period 1 (run-in) and Study Period 2 (intervention). During Study Period 1, CCI dosing and timing data in Glooko RMA will be masked to study participants and no dosage modifications will occur during Study Period 1, apart from acute complication occurring during that Study Period. Study participants will only be unmasked to the dosing and timing data in Glooko RMA during Study Period 2. Study personnel will be unmasked during both Study Period 1 and Study Period 2.

Study questionnaires will also be administered at multiple time points (Visit 1, Visit 3, and Visit 7) to provide baseline and endpoint data.

Additionally, the study will be conducted with participants in an outpatient setting with study interventions representative of standard clinical practices, to minimise bias associated with participation in a clinical trial.

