- Total insulin dose per day, basal dose and insulin dose per type of meal (breakfast [B], lunch [L], snacks, and dinner [D]) as well as corrections doses
- Occurrence, change, and masked versus unmasked change in correction boluses
- CGM curves integrated with data received from the Tempo Pen to examine the association between MBD and TIR, TAR, TBR, and HbA1c
- CGM curves integrated with data received from the Tempo Pen to examine the association between mistimed bolus and TIR, TAR, TBR, and HbA1c
- Participant and healthcare professional (HCP) questionnaires.

Exploratory

- To evaluate change in HbA1c from baseline to Visit 7.
- To evaluate change in HCP views on a connected diabetes management platform.
- To evaluate change in participant views on a connected diabetes management platform.
- To carry out analysis for calculation of MBDs.

- Summary statistics of actual and change in HbA1c between baseline and Visit 7
- Outcome of Study F3Z-MC-IORW (IORW) HCP questionnaires
- Outcome of Study IORW participant questionnaires
- CGM curves integrated with data received from the Tempo Pen/Smart Button

Objectives

- To determine participant interaction with the mobile application and its correlation with MBD change between Study Period 1 versus Study Period 2.
- To determine participant CGM wear time and correlation with MBD change between Study Period 1 versus Study Period 2.
- To evaluate participant's fear of hypoglycaemia and its correlation with MBD.
- To evaluate participant's daytime and nighttime CGM profiles during the 2 periods.

Endpoints

- Glooko Mobile Application use data (for example, number of connections to the application, number of uploads from CGM, number of CCI data coming from Tempo Smart Button, % of CGM data available, and number of manual insulin dose records) and comparison of Study Period 1 and Study Period 2 application use
- Summary of CGM wear time data and correlation with MBD data and differences between Study Period 1 versus Study Period 2
- Hypoglycaemia Fear Survey Short Form (HFS-SF) questionnaire scores will be summarized between Visit 1 and Visit 7 and correlated with MBD data.
- Summarize nighttime (0000 hours to 0600 hours) versus daytime CGM profiles during the masked/unmasked periods.

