6.2. Appendix 2: Timing of Assessments and Events for Analysis

Study Day 1 is the date in which the participants start Visit 1. Study days will be calculated as follows:

 $Pre\ first\ usage,\ study\ days = event\ date - Visit\ 1\ date$

On the day of or post data upload, study days = event date -Visit 1 date +1

The initial 4 weeks of the study will be used to allow participants to reach a routine before the baseline data assessment. Therefore, unless otherwise stated, data collected from the last 2 weeks of the masked period (Study Period 1, Weeks 5 and 6) will be used as baseline. Data from the last 4 weeks of the unmasked period (Study Period 2, Weeks 15 to 18) will be used for endpoint, in other words, 2 weeks prior to Visit 3 (face-to-face) and 4 weeks prior to Visit 7 (face-to-face) will be used. Data from these specified timepoints will be used to assess the primary and secondary objectives.

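### The exploratory change in fear of hypoglycaemia is calculated only from Visit 1 to Visit 7, so it cannot separate the masked run-in from the unmasked period, although a Visit 3 score is collected just before unmasking

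*SAP*

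**What the plan says.** **Analysis.** SAP 4.5.7 states that the HFS-SF score "will be summarized at Visit 1 and Visit 7 and change will be calculated" and that scores will be analysed with MBD data by Spearman correlation. The endpoint in SAP 1.1 reads "questionnaire scores will be summarized between Visit 1 and Visit 7 and correlated with MBD data". Exploratory endpoint 7 in Protocol Table 3.1 reads "HFS-SF questionnaire score between Visit 1 and Visit 7 and MBD data". Neither document plans an analysis of the Visit 3 score.

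**Collection.** The Schedule of Activities (Protocol Table 1.1) marks HFS-SF at Visits 1, 3 and 7 and at early termination. Under Protocol 4.2.2.2 the Visit 1 form comes before the pen, button and app are shown to the participant. Under Protocol 4.2.4 staff unmask the data at Visit 3 only "following completion of the IORW Participant Visit 3 Questionnaire and HFS-SF Questionnaire".

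**Baseline.** Protocol 4.1.1 gives the baseline label to both the Visit 1 and the Visit 3 questionnaires. Protocol 6.3 says: "Study questionnaires will also be administered at multiple time points (Visit 1, Visit 3, and Visit 7) to provide baseline and endpoint data". For the other participant questionnaires, SAP 4.4.1.1.10 and 4.5.3 use Visits 1, 3 and 7 in shift tables. For the primary and secondary objectives, SAP 6.2 sets a default: "data collected from the last 2 weeks of the masked period (Study Period 1, Weeks 5 and 6) will be used as baseline".

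**The concern.** Participants serve as their own control, and the contrast of interest is masked against unmasked. A questionnaire completed just before unmasking is the natural start for a change over the unmasked period, and the protocol takes care to obtain one. The planned analysis passes over it and starts six weeks earlier, before the participant has used any part of the study platform.

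Between Visit 1 and Visit 3 the participant starts the study pen, button and app, is given guidance on using real-time CGM readings, and is trained on hypoglycaemia. Some also change rapid-acting insulin or CGM model. The training and the CGM guidance could plausibly move a fear-of-hypoglycaemia score by themselves. With only the planned change reported, a reader of the study report could not tell whether a movement in the score happened during run-in, after unmasking, or in both periods.

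**Working it through.** No power or sample size figure is involved. The check is one of visit timing and of what the planned change contains.

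**1. Visit timing.** The inputs are the nominal intervals between visits in Protocol Table 1.1.

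- Visit 1 to Visit 3: 1 + 5 = 6 weeks, masked.
- Visit 3 to Visit 7: 1 + 3 + 4 + 4 = 12 weeks, unmasked.
- Visit 1 to Visit 7: 6 + 12 = 18 weeks, which agrees with the study duration in Protocol 4.4.1.
- Share of the planned interval before unmasking: 6 / 18 = 33%.

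**2. What the planned change contains.** Write H1, H3 and H7 for a participant's HFS-SF score at Visits 1, 3 and 7. Then

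H7 − H1 = (H3 − H1) + (H7 − H3),

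that is, overall change = run-in change + unmasked-period change. The plan reports only the left-hand side. Any given value of it fits a shift wholly in the run-in, a shift wholly after unmasking, or two shifts of opposite sign. H3 is the one number needed to separate the two terms, and it is already collected.

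**3. What falls within H3 − H1.**

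- Start of the study pen, button and app (Protocol 4.2.2.2).
- Guidance on real-time CGM use and hypoglycaemia training at Visit 1 (Protocol 4.2.2.2).
- A switch to Humalog or to the Dexcom G6, for those not already using them (Protocol 4.2.2.2 and 4.4.2).

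Protocol 4.4.2 gives the first four weeks of run-in as time to adjust to these changes. SAP 6.2 therefore leaves those weeks out of the baseline for the primary and secondary endpoints.

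**4. Alignment with the MBD change.** By SAP 4.3.2 and 6.2 the MBD change runs from Weeks 5–6, ending at Visit 3, to Weeks 15–18, ending at Visit 7. The HFS-SF change that ends at the same two visits is H7 − H3. The planned H7 − H1 starts 6 weeks before Visit 3.

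**5. What is correlated.** SAP 4.5.7 speaks of scores and MBD data. In Protocol Table 3.1, exploratory objectives 5 (app interaction) and 6 (CGM wear time) refer to correlation with MBD change, while objective 7 (fear of hypoglycaemia) refers to MBD alone. SAP 1.1 keeps that difference. Whether scores or changes enter the correlation, and from which MBD period, is therefore not stated.

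**The case against.** The strongest reply is that Visit 1 to Visit 7 is a deliberate and legitimate choice. It stands consistently in Protocol Table 3.1, SAP 1.1 and SAP 4.5.7. Visit 1 is one of the two visits whose questionnaires carry the baseline label, and it gives the only score taken before any exposure to the platform. Protocol Table 6.2 lists the platform in both study periods, so a Visit 1 to Visit 7 change answers a fair descriptive question about the platform as a whole. The Weeks 5–6 default in SAP 6.2 yields where the SAP says otherwise, and it serves the primary and secondary objectives; HFS-SF is exploratory. All of this stands, and it is why the Visit 1 to Visit 7 change should be kept.

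The run-in contrast is also limited. Inclusion criterion 5 requires current CGM use, some participants may already use Humalog or the Dexcom G6, and the Schedule of Activities repeats hypoglycaemia training at Visits 3, 5 and 6 if required. That stands too. One third is a share of calendar time, not of any change in score.

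Two stronger readings are tempting and are not supported:

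- A reader might infer that an 18-week fear change will be correlated with a 12-week MBD change and that the correlation will be weakened. The SAP does not say that changes are correlated. Even if they were, nothing in the documents shows whether including the run-in would lower or raise the coefficient.
- A reader might infer that the plan credits run-in effects to unmasking. Neither document says that the HFS-SF change will be attributed to unmasking.

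None of this explains why a score collected at Visit 3, before unmasking, has no planned use while the other participant questionnaires do use Visit 3.

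**Conclusion.** The point holds as a small, low-cost improvement to an exploratory endpoint. The only planned HFS-SF change joins 6 masked and 12 unmasked weeks and cannot separate them, although the score that would do so is collected. Protocol and SAP agree with each other here, so this is a limitation of the analysis and not a contradiction.

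The size of any run-in shift cannot be derived from the documents. The mismatch with the MBD interval arises only if changes are correlated, which the SAP leaves open. The primary result is unaffected.

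The Visit 3 to Visit 7 change would still be an uncontrolled before-after change in a single arm. In addition, the Visit 7 form is completed after the data review with the participant (Protocol 4.2.7), whereas the Visit 3 form comes before it.

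**What to change.** In SAP 4.5.7:

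- Summarise HFS-SF at Visits 1, 3 and 7.
- Report three changes: Visit 1 to Visit 3 (run-in), Visit 3 to Visit 7 (unmasked period) and Visit 1 to Visit 7 (overall, as now planned).
- State whether the Spearman correlation uses scores or changes, and which MBD period. If changes are correlated, pair the Visit 3 to Visit 7 HFS-SF change with the MBD change from Weeks 5–6 to Weeks 15–18.

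Align the endpoint wording in SAP 1.1 and, at the next opportunity, in Protocol Table 3.1. Protocol 9.3 and SAP 4.1 already allow additional exploratory analyses and call for an amendment only when a principal feature changes, so adding the Visit 3 rows should not need one by itself; the change would be described in the clinical study report. The cost is a short SAP edit and a few extra output rows. No new data collection is needed.

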4.5.8. Summary Statistics for Daytime and Nighttime Continuous Glucose Monitoring Profiles

Summary of daytime CGM profiles and summary of nighttime (0000 to 0600 hours) CGM profiles for Study Period 1 and Study Period 2.

4.6. Other Safety Analyses

Analyses of AEs will be descriptive and include all data collected during the treatment period. All AEs will be coded using the standardized Medical Dictionary for Regulatory Activities (MedDRA) central coding dictionary, version 24.1 or greater. Safety analysis and all analyses of adverse events will be carried out on the safety population.

4.6.1. Adverse Events

A table summary and listing and of all AEs will be generated which includes participant ID, System Organ Class (SOC), Preferred Term (PT), AE start date and study day, AE end date and study day, severity of AEs, seriousness of AEs, AE relatedness, action taken, and AE outcome. Additionally, a listing and table summary of unanticipated adverse device effects (UADEs) will be provided.

A separate table will be generated by SOC and PT for all the AEs. It will be represented in decreasing order of frequency by SOC and PT.

Serious adverse events

A table summary and listing of all serious adverse events (SAEs) will be generated which includes participant ID, SOC, PT, AE start date and study day, AE end date and study day, severity of AEs, AE relatedness, action taken, AE outcome, and SAE criteria.

Adverse events reported as reason for discontinuation from study

A table summary and listing of all AEs reported as reason for discontinuation will be generated which includes participant ID, SOC, PT, AE start date and study day, AE end date and study day, severity of AEs, seriousness of AEs, AE relatedness, action taken, and AE outcome.

Unanticipated adverse device events

A UADE is a serious adverse effect on health or safety or any life-threatening problem or death caused by or associated with a device, if that effect, problem, or death was not previously identified in nature, severity, or degree of incidence in the investigational plan or application (including a supplementary plan or application), or any other unanticipated serious problem associated with a device that relates to the rights, safety, or welfare of the participant.

A listing and table summary of UADEs will be provided.

4.6.2. Narratives

The following are "notable" events, from start of study intervention through end of study participation (or data cutoff for the submission if earlier):

- deaths
- SAEs, and
- permanent discontinuations of study intervention due to AEs.

Narratives (participant-level data and summary paragraph) will be provided for participants in the safety population with at least 1 notable event.

Safety topics of interest are not considered notable events, unless 1 of the above criteria is met. Displays with individual participant-level data will be created for safety topics of interest using various formats such as a customized listing and/or a customized graphical participant profile as specified in the section associated with the safety topic of interest. Medical case summaries or vignettes will be provided if deemed relevant for the discussion of the safety topic of interest.

4.6.3. Device Product Complaints

A listing of device deficiencies and device product complaints will be generated and the date, description of the device deficiency, and any associated AEs will be included, if applicable.

4.6.4. Hypoglycemic Events

The number of hypoglycemic events (CGM levels below the threshold for at least 15 minutes) will be summarized by study period in a table (Danne 2017). A data listing will also be generated. The number of Level 1 (\leq 70 mg/dL) and Level 2 (\leq 54 mg/dL) sensor detected hypoglycemic events will be summarized in a table, as well as participant-reported hypoglycemia if available.

Level 3 hypoglycemic events, which are considered as SAEs, will also be summarized and listed.

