## 1.3. Schedule of Activities

Table 1.1 summarises the Schedule of Activities (SoA) for the study.

Table 1.1. Schedule of Activities for Study F3Z-MC-IORW

	Study Pe	eriod 1 (Masl	ked)	Stu	Study Period 2 (Unmasked)				UNS	ET
Visit Number	V1	V2	V3	V4	V5	V6	V7	V8 or ET(Exit)		
Visit Type	On-site	Remote	On-site	Remote	Remote	Remote	On-site	Remote		
Time from previous visit (weeks or days)	N/A	1 W	5 W	1 W	3 W	4 W	4 W	3D	N/A	N/A
Visit window (days)	N/A	+/-3	+7	+/-3	+/-3	+/-3	+7	+/-1	N/A	N/A
Study Logistics	-	 		<del>-</del>	-				-	
Informed Consent signed	X									
Eligibility Criteria Reviewed	X									
Enrolment	X									
Install and set-up Glooko RMA	X									
Pair the Tempo Smart Button	X									
Study CGM device user training provided	X									
Study phone user training provided	X									
Complete Participant Training	X									
Participant brings mobile device with RMA and Tempo Pen with Tempo Smart Button			X				X			X
Confirm Tempo Smart Button transfer onto Glooko RMA			$X^1$		$X^1$	X 	$X^1$		X 	X 
Review the functioning, understanding, and use of the study platform components	X	X	X	X	$X^2$	$X^2$			$X^2$	

	Study Per	Period 1 (Masked)			ıdy Period	2 (Unmask	ed)	Follow-up	UNS	ET
Visit Number	V1	V2	V3	V4	V5	V6	V7	V8 or ET(Exit)		
Visit Type	On-site	Remote	On-site	Remote	Remote	Remote	On-site	Remote		
Time from previous visit (weeks or days)	N/A	1 W	5 W	1 W	3 W	4 W	4 W	3D	N/A	N/A
Visit window (days)	N/A	+/-3	+7	+/-3	+/-3	+/-3	+7	+/-1	N/A	N/A
Unmask Tempo Pen data in Glooko RMA			X							
Clinical Assessment and Diab	etes Management									
Medical History (including pre-existing conditions)	X									
Demographic information	X									
Height and Weight	X		$X^3$				$X^3$			$X^3$
Physical Examination	X									
Urine PoC Pregnancy Test (WOCBP only)	X									
HbA1c PoC Test	X						X			X
Vital Signs	X									
Hypoglycaemia management and training	X		$X^4$		$X^4$	$X^4$			X 	QR
Review concomitant medications	X	X	X	X	X	X	X	X	X	X
Review Adverse Events	X	X	X	X	X	X	X	X	X	X
Review Device Deficiencies (DD)	X	X	X	X	X	X	X	X	X	X
Review of glucose values and insulin regimen with participant (adjust if appropriate)	X		X 		X 	$X^5$	X 			X 
Document any educational activities			$X^6$		$X^6$	$X^6$	$X^6$			$X^6$
Study Material Management										
Dispense Tempo Smart Button	X								X 	
Dispense Humalog Tempo Pens	X		X						X 	

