1.2. Study Design

1.2.1. Overall Design

Study F3Z-MC-IORW (IORW) is a multicenter, open-label, controlled, single-arm pragmatic outpatient study in participants with T1D or T2D that comprises of 2 study periods, including:

- a 6-week run-in period (Study Period 1) when insulin timing and dosage data

 CCl is masked to the participant using the Glooko® Research Mobile Application (RMA) and is unmasked to the healthcare professional (HCP) using the Glooko HCP platform, and
- a 12-week intervention period (Study Period 2) when insulin timing and dosage data

[figure not shown]
 CCI is unmasked to the participant using the Glooko RMA and the HCP using the Glooko HCP platform.

Study IORW will be carried out in France and will include up to 10 clinical study sites. The study is expected to last approximately 16 months, with each participant duration of approximately 18 weeks. Approximately 50 participants will be enrolled in the study. Best efforts will be made to enroll a participant ratio of 4:1 for participants with T1D to participants with T2D.

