1.2.1.1. Study Period 1 (Run-in) – Weeks 1 to 6 (Baseline)

Following the screening, the participants who meet study criteria will:

- receive sponsor-provided Humalog® Tempo™ Pen and Tempo Smart Button, Dexcom G6 Continuous Glucose Monitoring (CGM) system, and study-specific Android smartphone, and
- be instructed on how to use the study platform and will receive guidance from the study team on the use of the real time CGM data on the receiver to help them manage diabetes and insulin dosing. They will be trained on how to upload their CGM data on the Glooko RMA.

Participants will be asked to follow their pre-insulin study regimen (as prescribed by the investigators), lifestyle, and behavior. It is recommended that the site does not interact with the participant with respect to their Glooko RMA during the masked Study Period 1 unless required for participant safety. The study participant and HCP will not communicate, outside of the scheduled visit and activities, except in cases of acute complication, adverse event (AE) and device deficiency (DD) reporting, or need for technical support.

Following Study Period 1 (during Visit 3), mealtime insulin timing and dosage data

will be unmasked to the study
participant by the HCP. The study participant and HCP will then review and discuss together the
data collected during Study Period 1, including the potential reasons for suboptimal glucose
control. The HCP will be able to propose any educational activities to be taken during Study
Period 2 that would result from the review of the Glooko platform report, including insulin dose
adjustments and other advices deemed appropriate (for example, missing bolus doses, late
injection timing, and carb counting).

1.2.1.2. Study Period 2 (Intervention) – Weeks 7 to 18

Following Study Period 1, the participants will enter the 12-week Study Period 2 during which insulin timing and dosage data CCI will be visible (unmasked) to the participant and HCP in the Glooko RMA and HCP platform.

Throughout the entire Study Period 2, data from the Humalog Tempo Pen/Smart Button will be transferred to the Glooko RMA. Participants should continue to periodically upload Dexcom G6 CGM during Study Period 2.

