2.1. Multiplicity Adjustment

A p-value of \leq 0.05 will be considered statistically significant. No adjustments for multiplicity will take place.

3. Analysis Sets

For the purposes of analysis, the following analysis sets are defined:

Participant Analysis Set	Description			
Main Analysis Set	All continuous glucose monitoring (CGM) data should be included in the final analysis, but the proportion of participants who met the minimum 70% data-obtainment requirement during 14 days should be reported as part of the data completeness. Participants with ≥70% of CGM data present for a particular day will be considered complete for the day or valid CGM day. Similarly daytime and nighttime periods will be checked separately for valid CGM period. Following the guidelines of the Advanced Technologies and Treatments for Diabetes (ATTD) consensus on CGM use, only participants with at least 10 days' worth of valid CGM data out of the last 14 days (Weeks 5 and 6) in the masked application period will be considered for the main analysis set (Danne et al. 2017; Battelino et al. 2023).			
	Among these participants, only participants that satisfy the below criteria for the unmasked application period will be considered as evaluable participants and included in the main analysis set:			
	 participants with at least 20 of 28 days' worth of CGM data (Weeks 15 to 18), or participants discontinuing early that have at least 20 days' worth of CGM data in the whole unmasked application period (Weeks 7 to 18). 			
	Efficacy analyses will be carried out on the main analysis set. To allow for this clinical trial to be generalizable to the wider population and to prevent the chance of analyzing a biased set of "only adherent" participants, efficacy analyses will be repeated on the sensitivity analysis set.			
Sensitivity Analysis Set	The sensitivity analysis set includes all participants in the main analysis set, plus participants with at least 10 days' worth of CGM data in the whole masked application period (Weeks 1 to 6), and all participants with at least 20 days' worth of CGM data in the whole unmasked application period (Weeks 7 to 18).			
Safety Analysis Set	Safety analyses will be carried out on the Safety Population, which consists of all participants with at least 1 measurement in the masked application period and/or unmasked application period.			

4. Statistical Analyses

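### SAP 4.6.4 compares counts of CGM-detected hypoglycaemic events between a 6-week and a 12-week period with no exposure denominator (minor)

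*SAP*

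**What the plan says.** SAP 4.6.4 plans this display of sensor-detected events: "The number of hypoglycemic events (CGM levels below the threshold for at least 15 minutes) will be summarized by study period in a table". It adds a listing, and a table of Level 1 and Level 2 events. No sentence in the section mentions a rate, person-time or CGM days. Protocol 9.3.3 likewise plans only descriptive statistics.

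The periods differ in length. SAP 1.2.1 describes "a 6-week run-in period (Study Period 1") and "a 12-week intervention period (Study Period 2").

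The population is the safety set: "Safety analysis and all analyses of adverse events will be carried out on the safety population" (SAP 4.6). SAP 3 defines that set as "all participants with at least 1 measurement in the masked application period and/or unmasked application period", so no minimum amount of CGM data is required in either period.

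For the primary endpoint the SAP does scale by exposure. SAP 4.3.1.1 divides each participant's missed boluses by the days with evaluable CGM data and multiplies by 7.

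**The concern.** A count grows with the time observed. With one period twice as long as the other, the two columns of this table are not on the same scale.

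This matters more than usual here because the study has one arm and participants act as their own control (Protocol 6.3), so Period 1 is the only comparator for safety. Hypoglycaemia is a named risk of the platform (Protocol 2.4.2), and investigator insulin adjustment is restricted in Period 1 but allowed in Period 2 (Protocol 6.1). Readers will want to know whether hypoglycaemia became more or less frequent after unmasking. Raw counts side by side could suggest a rise where there is none, or hide a real fall.

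The app-use counts in SAP 4.5.5 (connections, uploads and similar items) have the same gap on a smaller scale. They are tabulated by period without a denominator, although comparing use between the periods is a stated exploratory endpoint in SAP 1.1.

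**Working it through.** **1. Period lengths.** The intervals in the Protocol 1.3 schedule reproduce the stated lengths.
- Period 1 (Visit 1 to Visit 3): 1 + 5 = 6 weeks = 42 days.
- Period 2 (Visit 3 to Visit 7): 1 + 3 + 4 + 4 = 12 weeks = 84 days.

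**2. Count ratio.** Expected count = event rate × time observed. Hence

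Period 2 count / Period 1 count = (rate ratio) × (Period 2 exposure / Period 1 exposure).

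At nominal lengths, equal wear and full retention, the exposure ratio is 84/42 = 2.0.

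| True rate ratio, Period 2 / Period 1 | Count ratio shown |
|---|---|
| 1.00 (unchanged) | 2.0 × 1.00 = 2.0 |
| 0.75 (25% fall) | 2.0 × 0.75 = 1.5 |
| 0.50 (50% fall) | 2.0 × 0.50 = 1.0 |

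For example, an assumed constant rate of 1 event per week gives 6 events per participant in Period 1 and 12 in Period 2.

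**3. Which weeks count.** Whole periods is the natural reading, because SAP 6.2 ties the shorter windows to the primary and secondary objectives. If Weeks 5–6 and 15–18 were used instead, the ratio would be 4/2 = 2.0 as well.

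**4. Visit windows.** The schedule's row "Visit window (days") allows +7 days at Visits 3 and 7. With an unchanged rate and the other intervals on schedule:
- Visit 3 late: 84/49 = 1.71
- Visit 7 late: 91/42 = 2.17
- both late: 91/49 = 1.86

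**5. Retention.** SAP 5 assumes a 35% dropout rate, in an item that also refers to missing CGM data. Suppose, as an assumption, that all of it is dropout in Period 2 and the rate is unchanged. For pooled totals:
- all leave at Visit 3: 2.0 × (1 − 0.35) = 1.30
- leaving spread evenly over Period 2: 2.0 × (1 − 0.35/2) = 1.65

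A per-participant mean need not fall in this way. Participants who leave at Visit 3, for instance, would not enter a Period 2 mean taken over those who contribute.

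**6. With a denominator.** Using events / evaluable CGM days × 7, an unchanged rate gives a Period 2 / Period 1 ratio of 1.0 in every case above.

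**The case against.** The strongest reply is that little depends on this table. It is descriptive, these events are not an endpoint, no test uses the counts, and the period lengths are stated prominently. Time below range is a percentage, so it does not depend on period length. It is analysed in the main analysis set (SAP 4.4), and SAP 4.1 repeats the efficacy analyses on the sensitivity set.

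Other outputs bear on exposure:
- disposition by study period in the safety population, with a listing of the week of discontinuation (SAP 4.2);
- the percentage of CGM data available, by period (SAP 4.5.5);
- CGM wear time by period (SAP 4.5.6);
- descriptive exploration of CGM days and dropout in the unmasked period (SAP 4.8.1);
- for app use, exposure to the app by period and overall (Protocol 9.3.4).

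All of this stands, and it is why the point is minor. A reader could rescale approximately. But time below range is a share of time in selected weeks and not an event rate, and none of these outputs puts a rate in the hypoglycaemia table.

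Two stronger readings are tempting but not supported:
- **Levels 1 and 2.** A reader might infer that these counts are also set side by side by period. Only the first sentence of SAP 4.6.4 refers to study period; the Level 1 and Level 2 sentence does not.
- **A bound on the wear effect.** A reader might take the evaluability floor ("participants with at least 20 of 28 days' worth of CGM data (Weeks 15 to 18"), or 20/28 = 71%) and infer a ratio between 2.0 × 0.714 = 1.43 and 2.0/0.714 = 2.80. That floor belongs to the main analysis set. The safety set has no floor, so the range does not bound this table, and the documents give no wear data from which to derive one.

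**Conclusion.** The point holds as a minor one. As written, the by-period table of CGM-detected hypoglycaemic events lacks a common scale. The ratio of 2.0 at an unchanged rate rests on nominal lengths, equal CGM wear and full retention, and does not depend on which analysis weeks are meant. Late visits alone give 1.71 to 2.17. Placing the whole assumed 35% loss in Period 2 gives about 1.30 to 1.65 for pooled totals.

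A reader might infer that the published table will necessarily show a doubling, or that the plan's safety conclusions are unsound. Neither follows. The size of the distortion depends on retention and wear that are not yet known, and no inference in the plan uses these counts. That uncertainty is itself the reason to use observed exposure and not a fixed factor of two.

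**What to change.** In SAP 4.6.4, report CGM-detected hypoglycaemic events per evaluable CGM week by study period, using the denominator approach of SAP 4.3.1.1: events / days with evaluable CGM data × 7. Show the CGM exposure beside the counts. Apply the same to the Level 1 and Level 2 counts if these are shown by period.

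Secondary: in SAP 4.5.5, give the app-use counts per participant-week by period. The percentages there need no change.

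Cost: SAP or table-shell wording and a derived column. The CGM days come from data already processed for missed boluses and wear time. No new data collection and no change to the design or to any test is needed.
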